#### B. For non-injected target lesions

- As long as the non-injected target lesions remain non-injected, the non-injected target SOD is compared with measurements obtained prior to C1D1. If any non-injected target lesion must be injected (eg, because disappearance of other injected target lesions or because of inaccessibility of other lesions), the maximal non-injected response has been achieved and any subsequent non-injected response is considered nonevaluable.

A lesion's injection status will be determined based on the ADU-S100 Administration page of the CRF which collects "Was this lesion injected at this visit?". If a lesion is reported as "Yes" at a specific time point, then the lesion is considered injected from that timepoint onwards. Prior to that injection timepoint, it will be considered non-injected. Once a lesion is injected, it will be considered an injected target lesion for all subsequent timepoints, even if it is not injected at a later timepoint.

#### 7.4.5 *Secondary Endpoint Analysis Methods*

The calculation of ORR and accompanying CI will be repeated for the EAS. The secondary efficacy endpoints described in [Section 6.4.1.2](#) will be summarized for the All Treated Population.

Overall survival and PFS will be analyzed with standard survival methods (Kaplan-Meier estimates) to include the number of subjects who are alive at data cut-off, number of subjects censored, percentiles (including 95% CIs determined by the Brookmeyer and Crowley method) and range. Kaplan-Meier summaries, including graphs of survival curves, will be generated for all subjects receiving study drug.

Progression-free survival at 6, 12, and 24 months (including 95% CIs determined by Greenwood’s formula), DOR, and DODC will be analyzed with the same statistical methodologies as applied to OS.

DCR will be calculated along with accompanying CIs, similar to ORR.

Censoring rules for the analysis of each endpoint are described in [Section 7.4.6.2](#). Subgroup analysis is described in [Section 7.4.6.8](#).

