### 12.5.2 Secondary Efficacy Endpoints

Secondary efficacy endpoints are defined as:

**Overall Survival (OS)** is defined as the time from first dose of study drug until date of death due to any cause. Subjects without documentation of death at the time of analysis will be censored as of the date the subject was last known to be alive.

**Progression-free survival (PFS)** is defined as the time from first dose of study drug to first documentation of disease progression or death due to any cause. Subjects who do not experience progressive disease and are alive will be censored at the time of last evaluable tumor assessment.

**Duration of response (DOR)** is defined as the time from the first tumor assessment that supports the subject's objective disease response to the time of disease progression or death due to any cause.

**Disease control rate (DCR)** is defined as subjects with CR, PR, or stable disease (SD).

**Duration of disease control (DODC)** is defined as the time from the first tumor assessment that supports the subject's disease control (CR, PR, SD) to the time of disease progression or death due to any cause.

**ORR** per iRECIST

RECIST v1.1 and iRECIST will be used for all secondary efficacy endpoints, as applicable. Estimates of PFS and OS will be assessed using Kaplan-Meier methodology.

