#### 6.5.1.2 *Secondary Efficacy Variables*

Secondary efficacy endpoints include the following:

- Overall Survival (OS): defined as the time from first dose of either study drug until date of death due to any cause. Subjects without documentation of death at the time of analysis will be censored as of the date the subject was last known to be alive.
- Progression-Free Survival (PFS): defined as the time from first dose of either study drug to first documentation of disease progression or death due to any cause. Subjects who do not experience progressive disease and are alive at the time of analysis will be censored at the time of last evaluable tumor assessment. Subjects who receive anti-cancer therapy prior to documented disease progression will be censored on the date of last evaluable tumor assessment on or prior to the start date of the anti-cancer therapy. Subjects with no on-treatment tumor assessments will be censored on the date of treatment start.
- Duration of Response (DOR): defined as the time from the first tumor assessment that supports the subject's objective disease response to the time of disease progression or death due to any cause. Subjects who have ongoing response at the time of analysis will be censored at the time of last evaluable tumor assessment. Subjects who receive anti-cancer therapy prior to documented disease progression will be censored on the date of last evaluable tumor assessment on or prior to the start date of the anti-cancer therapy. Subjects with no on-treatment tumor assessments will be censored on the date of treatment start.
- Disease Control Rate (DCR): defined as the proportion of subjects with CR, PR, or stable disease (SD).

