## 7.2 Analysis Populations

The analysis populations are defined as follows:

- **All Treated Population:** Includes all subjects who received any amount of either study drug.
- **Evaluable Analysis Set (EAS):** Includes all subjects who received any amount of either study drug and additionally who either have at least one evaluable response assessment or who discontinued the study for a reason of toxicity, clinical progression, or death.
- **Modified All Treated Population:** The protocol inclusion criteria require eligible subjects to be PD-L1 positive (defined as combined positive score [CPS]  $\geq 1$ ). If any subject with baseline CPS  $< 1$  were to be enrolled (a protocol deviation), then a Modified All Treated Population is defined as the All Treated Population excluding subjects with baseline CPS  $< 1$ .

Though subjects with baseline CPS  $< 1$  are not expected on study, if this were to occur, the Modified All Treated Population would be used for Efficacy summary analysis, rather than the All Treated Population. Otherwise, the All Treated Population will be used for both Efficacy and Safety analyses. Sensitivity analysis of efficacy on the EAS population will be presented only if there is a considerable difference between the EAS and the All Treated Population.

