**Table 3 Censoring Rules for OS, PFS, DOR, and DODC**

Endpoint	Situation	Date of Censoring
OS	No documentation of death	Date that the subject was last known to be alive
PFS, DODC	No progression and no death	Date of last evaluable tumor assessment
PFS, DODC	Anti-cancer therapy prior to documented disease progression	Date of last evaluable tumor assessment on or prior to the start date of the anti-cancer therapy
PFS, DODC, DOR	No on-treatment tumor assessment	Date of treatment start
DODC	Ongoing disease control at time of analysis	Date of last evaluable tumor assessment
DOR	Ongoing response	Date of last evaluable tumor assessment

No other missing data will be imputed.

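### SAP 6.5.1.2 and Table 3 give never-scanned subjects a censored DOR and DODC, although they can have no documented response or disease control

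*SAP*

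**What the plan says.** - **Population.** SAP 7.4.5 states that the secondary efficacy endpoints "will be summarized for the All Treated Population". SAP 7.2 defines that population: "Includes all subjects who received any amount of either study drug". Neither a scan nor a response is required.
- **Method.** In SAP 7.4.5, "DOR, and DODC will be analyzed with the same statistical methodologies as applied to OS", and Kaplan-Meier summaries "will be generated for all subjects receiving study drug". The listed outputs include the number censored, percentiles with confidence intervals, and the range.
- **Time origin.** SAP 6.5.1.2 defines DOR as "the time from the first tumor assessment that supports the" objective response, and Protocol 12.5.2 uses the same origin. DODC starts at the first assessment supporting CR, PR or SD. When the best response is SD, the SAP starts it at the baseline assessment (6.5.1.2, explained in 7.6).
- **Unscanned subjects.** The DOR and DODC bullets of SAP 6.5.1.2 each carry the sentence "Subjects with no on-treatment tumor assessments will be censored on the date of treatment start". Table 3 repeats the rule in one row covering PFS, DODC and DOR, headed "No on-treatment tumor assessment".

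**The concern.** DOR describes how long a documented response lasted, and DODC does the same for documented disease control. A subject dosed but never scanned on treatment has neither. For PFS, a censoring date for that subject makes sense, because PFS starts at first dose for everyone. For DOR and DODC the same rule can act only on subjects who do not belong in the analysis.

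In a DOR table, a censored subject is normally read as a responder still in response. Early failures who never reached a scan would therefore be shown in the most favourable category.

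Such subjects are foreseeable. The first post-baseline scan is at Cycle 4 Day 1 (3 cycles × 21 days = 63 days, or 9 weeks, with a 7-day early window). Both documents provide for subjects without a response evaluation, and the COVID-19 appendix of the protocol ranks imaging last among procedures. SAP 7.6 moves the efficacy analysis from the evaluable set (EAS) to All Treated, so every dosed, unscanned subject is in the parent population.

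**Working it through.** The documents state no figure on this point, so there is none to reproduce. The check sets the rules side by side and then illustrates the effect with assumed counts.

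**1. Who has a valid origin and a stated rule?**

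| Subject | DOR origin | DODC origin | Treatment-start censoring applies? |
|---|---|---|---|
| CR or PR | First supporting scan | First supporting scan | No |
| Best response SD | None | Baseline scan | No |
| Scanned, best response PD | None | None | No; handling unspecified |
| Never scanned on treatment | None | None (SD cannot be documented) | Yes, for both |

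The rule reaches only the last row. For DOR, scanned subjects with SD or PD have neither an origin nor a censoring row.

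**2. Effect on the DOR table (all counts assumed)**

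Literal reading: N = responders + never-scanned; censored = ongoing responders + never-scanned.

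- 5 responders (3 progressed, 2 ongoing) and 3 never scanned: N = 5 + 3 = 8 and censored = 2 + 3 = 5. Responders only: N = 5, censored = 2.
- 3 responders (1 ongoing) and 3 never scanned: N = 3 + 3 = 6 and censored = 1 + 3 = 4. Responders only: N = 3, censored = 1.

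For scale, among 20 treated subjects the expected number of responders is 20 × 0.19 = 3.8 at the null ORR and 20 × 0.38 = 7.6 at the alternative. One or two extra subjects are visible in a table of that size.

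**3. Range minimum**

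SAP 7.1.4 counts days as later date − earlier date + 1 when the earlier date is on or after dosing. If treatment start is taken as the origin, the duration is 0 + 1 = 1 day. The SAP does not name that origin for DOR; under the stated origin the duration is undefined.

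**4. Kaplan-Meier median**

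The estimate is the product over event times of (1 − d/n), where n counts subjects with time at or beyond that event time. A subject censored before the first event is in no n. Take hypothetical responders with events at 4, 6 and 12 months and one censored at 9 months:

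- S(4) = 3/4
- S(6) = 3/4 × 2/3 = 1/2, so the median is 6.0 months with N = 4 and 1 censored.

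Adding 1, 2 or 3 subjects censored at 1 day gives N = 5, 6 or 7 and 2, 3 or 4 censored. The median stays at 6.0 months each time.

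**5. Why the missing restriction also matters**

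Suppose a programmer filled the gap by counting scanned non-responders from treatment start with progression as an event. With 8 such subjects progressing at week 9 (63/30.4375 = 2.07 months) added to the same four responders, S(2.07) = 1 − 8/12 = 0.33 and the median falls to 2.1 months. The SAP does not prescribe this. The example shows only that leaving the subset unnamed is a larger risk than the unscanned rule itself.

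**The case against.** The strongest reply is that the definitions already select the subjects. DOR refers to a subject's objective response and DODC to a subject's disease control, so the All Treated sentence names only the parent population. The unscanned sentence would then be PFS wording repeated without effect. The table templates are in a separate document, so the printed N is unknown. All results are descriptive, sparse analyses may be dropped (Protocol 12.2), and subject listings and a swimmer plot would show who responded. The EOT scan, required when more than 6 weeks have passed since the last evaluation, may shrink the unscanned group if it counts as on-treatment.

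This limits the consequence but does not remove the rule. The SAP names DOR and DODC in the Table 3 row and repeats the rule in both bullets. A programmer following the text would include these subjects.

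A reader might infer more than the documents support:

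- **That all non-responders enter the tables as censored.** The rule covers only never-scanned subjects. For DODC, best response SD is validly included.
- **That censoring precedes any possible origin for both endpoints.** This holds for DOR. The SAP allows baseline as a DODC origin, and baseline precedes treatment start.
- **That the median duration is biased.** Step 4 shows that this rule leaves it unchanged.
- **That a misleading percent censored or number at risk is a planned output.** SAP 7.4.5 and Protocol 12.2 list the number censored, but neither of those quantities.

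**Conclusion.** Wrong as written, and minor. SAP 6.5.1.2 and Table 3 assign a censored DOR and DODC to subjects who can have neither, and SAP 7.4.5 contains no restriction that would exclude them. Read literally, each never-scanned subject adds one to the N and one to the number censored. If treatment start is assumed as the origin, the range minimum falls to about 1 day. The Kaplan-Meier median is unaffected.

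The size depends on how many dosed subjects are never scanned, which the documents do not give; the counts above are assumptions. The DOR handling of scanned non-responders is a separate gap that the same fix closes.

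**What to change.** 1. In SAP 7.4.5, state that DOR is analysed only in subjects with an objective response (CR/PR, or iCR/iPR), and DODC only in subjects with disease control (CR/PR/SD, or iCR/iPR/iSD), separately for RECIST v1.1 and iRECIST. The DOR and DODC table Ns should then equal the ORR and DCR numerators under the same criteria and population, which gives a simple programming check.
2. In Table 3, keep only PFS in the row for subjects without an on-treatment assessment.
3. Delete the matching sentences from the DOR and DODC bullets of SAP 6.5.1.2. The PFS sentence is not affected by this point.
4. While editing 7.4.5, correct its cross-reference for the secondary endpoints: it points to 6.4.1.2, but they are in 6.5.1.2.

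Returning to the EAS would not be a substitute. The protocol's EAS admits subjects who discontinued for toxicity without a scan, and the SAP's version adds clinical progression and death.

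The cost is SAP wording only, with no change to data collection. The reported N and number censored become smaller if any dosed subject was never scanned.

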### 7.4.6 Statistical/Analytical Issues

#### 7.4.6.1 Adjustments for Covariates

There are no planned applications of covariate adjustments; all statistical results are descriptive in nature.

#### 7.4.6.2 Handling of Dropouts or Missing Data

Censoring rules for the analysis of each secondary endpoint are summarized in [Table 3](#) shown on the next page.

**Table 3 Censoring Rules for OS, PFS, DOR, and DODC**

Endpoint	Situation	Date of Censoring
OS	No documentation of death	Date that the subject was last known to be alive
PFS, DODC	No progression and no death	Date of last evaluable tumor assessment
PFS, DODC	Anti-cancer therapy prior to documented disease progression	Date of last evaluable tumor assessment on or prior to the start date of the anti-cancer therapy
PFS, DODC, DOR	No on-treatment tumor assessment	Date of treatment start
DODC	Ongoing disease control at time of analysis	Date of last evaluable tumor assessment
DOR	Ongoing response	Date of last evaluable tumor assessment

No other missing data will be imputed.

#### 7.4.6.3 iRECIST Response Assessment

iRECIST is based on RECIST criteria. There are no changes compared to RECIST to the recommendations regarding the method of measurement. All responses per iRECIST have a prefix of “i” (ie, immune)—eg, “immune” complete response (iCR) or partial response (iPR),

and unconfirmed progressive disease (iUPD) or confirmed progressive disease (iCPD) to differentiate them from responses assigned using RECIST 1.1. Similar nomenclature is used for stable disease (iSD).

The iRECIST response assessment allows for the occurrence of pseudoprogression where a subject may appear to worsen before a delayed response occurs. Thus, instances of iRECIST progressive disease require confirmation. That is, if iUPD is not confirmed as iCPD, then the response effectively resets with the next iRECIST evaluation. In the event that no further response assessment follows the iUPD assessment (eg, subject was not judged to be clinically stable or subject refusal, protocol noncompliance, or death) or if all subsequent timepoint responses are iUPD, then date of iUPD can be used for analysis. Several examples of assignments of best overall response using iRECIST, are presented in [Table 4](#), adapted from the RECIST working group guidelines ([Seymour et al. 2017](#)).

**Table 4 Scenarios of Assignments of Best Overall Response using iRECIST**

	Timepoint Response 1	Timepoint Response 2	Timepoint Response 3	Timepoint Response 4	Timepoint Response 5	iBOR
Ex. 1	iCR	iCR, iUPD, or NE	iCR, iUPD, or NE	iUPD	iCPD	iCR
Ex. 2	iUPD	iPR, iSD, or NE	iCR	iCR, iUPD, or NE	iCR, iPR, iSD, iUPD, iCPD, or NE	iCR
Ex. 3	iUPD	iPR	iPR, iSD, iUPD, or NE	iPR, iSD, iUPD, NE, or iCPD	iPR, iSD, iUPD, NE, or iCPD	iPR
Ex. 4	iUPD	iSD or NE	iPR	iPR, iSD, iUPD, or NE	iPR, iSD, iUPD, iCPD, NE	iPR
Ex. 5	iUPD	iSD	iSD, iUPD, or NE	iSD, iUPD, iCPD, or NE	iSD, iUPD, iCPD, NE	iSD
Ex. 6	iUPD	iCPD	Any	Any	Any	iCPD
Ex. 7	iUPD	iUPD (no iCPD)	iCPD	Any	Any	iCPD
Ex. 8	iUPD	NE	NE	NE	NE	iUPD

Abbreviations for Table 4: iBOR = immune best overall response; iCPD = immune confirmed progressive disease; iCR = immune complete response; iPR = immune partial response; iSD = immune stable disease; iUPD = immune unconfirmed progressive disease; NE = not evaluable

#### 7.4.6.4 *Interim Analyses and Data Monitoring*

There are no interim analyses planned, nor is there a plan to establish a data monitoring committee for this study.

#### 7.4.6.5 *Multicenter Studies*

This is a multicenter study, with approximately 25 sites expected to participate. Efficacy data collected from all study sites will be pooled for data analysis. The effect of study site on the efficacy analysis results may be explored post-hoc, as needed.

#### 7.4.6.6 *Multiple Comparisons/Multiplicity*

There will be no adjustments for multiple comparisons in the efficacy analysis for this study. Results are descriptive in nature and there will be no formal comparisons made.

#### 7.4.6.7 *Active-Control Studies Intended to Show Equivalence*

This study does not include an active-control product and is not intended to demonstrate equivalence between any two drug products.

#### 7.4.6.8 *Examination of Subgroups*

Subgroup analysis provides further exploratory information. Subgroups may have small samples sizes insufficient for statistical inference, and statistical information such as CIs would be informational only. The ORR, OS, and PFS will be summarized by various subgroups of interest including combined positive score ( $1\% \leq \text{PD-L1 expression} < 20\%$  and  $\geq 20\%$  PD-L1 expression) and human papillomavirus (HPV) status.

Waterfall plots will be provided showing the best overall tumor response by primary tumor location and by disease status. A swimmer plot will be provided by primary tumor location and by disease status.

A forest plot showing the ORR of subgroups will be created for subgroups of interest provided that sufficient data are collected within the subgroups. Subgroups of interest could include the following characteristics: combined positive score ( $1 \leq \text{PD-L1 expression} < 20$  and  $\geq 20\%$  PD-L1 expression), HPV status, age ( $< 65$  years old and  $\geq 65$  years old), gender, race, ECOG performance status at baseline, disease stage at baseline, tobacco use, prior surgery, prior radiotherapy, site of primary tumor (larynx, oral cavity, oropharynx, hypopharynx, and all other [nasal cavity, paranasal sinuses, other]), and subsequent therapy.

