#### 10.2.3 Subsequent Anti-Cancer Therapy Follow-Up

At the EOT visit, any subsequent cancer-related therapy will be assessed until completion of the required safety reporting periods, death of the subject, withdrawal of consent, loss to follow-up, or close of study by the Sponsor.

All deaths must be reported on the eCRF.

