**Figure 1 ADU-CL-20 Study Design**

Subjects will be requested to complete multiple clinic visits during all dosing cycles. An end of treatment (EOT) visit will occur 30 (+7) days after the last dose of study drug. All EOT visit assessments will be completed prior to commencing any new anti-cancer therapy.

After completion of the EOT visit, follow-up visits will be conducted at 8-week intervals to satisfy protocol-specified safety reporting periods, and collect data on any subsequent cancer-related therapies as well as vital status. Follow-up visits may be conducted at the site or via telephone call, as appropriate.

Subjects who discontinue study drug early for reasons other than progressive disease will complete the EOT visit and will be asked to continue tumor response assessments. Follow-up visits will also be conducted at 8-week intervals for these subjects.

All study visits (and visit windows), assessments, and procedures will be performed as indicated in [Appendix A: Schedule of Events](#). On days when the study drug is administered, assessments will be performed prior to dosing unless otherwise specified.

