## 6.5 **Efficacy and Safety Variables**

### 6.5.1 *Efficacy Variables*

#### 6.5.1.1 *Primary Efficacy Variable*

The primary efficacy endpoint is the objective response rate (ORR) defined as the proportion of subjects in whom a complete response (CR) or a partial response (PR) is observed. The Response Evaluation Criteria in Solid Tumors (RECIST) v1.1 will be used to evaluate the primary efficacy endpoint. All responses will be confirmed at the subsequent tumor assessment.

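### The optional ORR forest plot may be split by subsequent therapy, the one listed factor that arises after treatment starts and can depend on response

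*SAP*

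**What the plan says.** SAP 7.4.6.8 opens by giving subgroup work a modest status: "Subgroup analysis provides further exploratory information". It warns that subgroups may be small and that confidence intervals are for information only. On the plot itself it says "A forest plot showing the ORR of subgroups will be created for subgroups of interest provided that sufficient data are collected within the subgroups". The list is permissive: "Subgroups of interest could include the following characteristics". It runs through combined positive score, HPV status, age, gender, race, baseline ECOG status, baseline disease stage, tobacco use, prior surgery and prior radiotherapy, then primary site, and closes with "and subsequent therapy".

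The outcome plotted is defined in SAP 6.5.1.1 as "the proportion of subjects in whom a complete response (CR) or a partial response (PR) is observed".

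Both documents place the recording of subsequent therapy late. Protocol 10.2.3 says "At the EOT visit, any subsequent cancer-related therapy will be assessed until completion of the required safety reporting periods". SAP 6.1 describes follow-up visits every 8 weeks after the End of Treatment (EOT) visit, which among other things "collect data on any subsequent cancer-related therapies as well as vital status". The SAP gives no definition of subsequent therapy as a subgroup, no time window for it, and no caution specific to it.

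**The concern.** A subgroup row on a forest plot invites the reader to ask which kind of patient responds better. That question makes sense only if membership of the subgroup was settled before the outcome could influence it. Subsequent therapy fails that condition. A subject normally starts other anti-cancer treatment after stopping study treatment, and one stated reason for stopping is confirmed progression. Group membership is therefore decided after the response data begin to accrue, and partly because of them.

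The row would sit beside valid baseline subgroups in the same display of the primary endpoint. The section's only caution is about small numbers. A reader told that intervals are wide is not thereby told that one row is conditioned on something downstream of the outcome. At stake is a misleading exploratory row; the trial's main result is not involved.

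**Working it through.** **Timing, from the documents**

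1. Listed factors. All items in SAP 7.4.6.8 except the last describe the subject at entry or the subject's history. SAP 7.4.2 counts smoking history as a baseline characteristic, so tobacco use belongs with them.
2. When other therapy can start. Protocol 9.6.1 does not permit non-study anti-cancer therapy for the disease during the study, and it lifts all prohibitions once the EOT visit is complete.
3. Why subjects reach that point. Protocol 8.3.2 lists confirmed progression among the reasons to stop treatment, alongside toxicity and the subject's own request. Under Protocol 9.4.2.3, a subject whose injected lesions regress until no lesion can be injected goes to the EOT visit and may carry on with pembrolizumab outside the trial.
4. How the documents treat later therapy elsewhere. SAP 6.5.1.2 and Table 3 in SAP 7.4.6.2 use it as a post-baseline event that triggers censoring for progression-free survival, duration of response and duration of disease control. Protocol 10.5 names it as a confounder when progression-free and overall survival are interpreted. Only SAP 7.4.6.8 uses it to define a subgroup.

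**Size, by illustration**

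The documents give no figure for this row, so there is none to reproduce. The one input taken from them is the null ORR of 0.19 (SAP 6.2). The uptake rates are assumptions.

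Let p be the true ORR, the same for everyone; a the probability of later therapy in responders; b the probability in non-responders. Then:

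- ORR with later therapy = p·a / [p·a + (1 − p)·b]
- ORR without later therapy = p·(1 − a) / [p·(1 − a) + (1 − p)·(1 − b)]

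With p = 0.19:

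| a | b | With later therapy | Without later therapy |
|---|---|---|---|
| 0.10 | 0.50 | 0.019/(0.019 + 0.405) = 4.5% | 0.171/(0.171 + 0.405) = 29.7% |
| 0.40 | 0.50 | 0.076/(0.076 + 0.405) = 15.8% | 0.114/(0.114 + 0.405) = 22.0% |
| 0.50 | 0.50 | 0.095/(0.095 + 0.405) = 19.0% | 0.095/(0.095 + 0.405) = 19.0% |
| 0.60 | 0.40 | 0.114/(0.114 + 0.324) = 26.0% | 0.076/(0.076 + 0.486) = 13.5% |

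At the alternative ORR of 0.38 with a = 0.10 and b = 0.50, the figures are 0.038/(0.038 + 0.310) = 10.9% and 0.342/(0.342 + 0.310) = 52.5%.

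No true heterogeneity was put into any line. Each gap comes only from the difference between a and b, and its sign follows which of the two is larger. The last line of the table could arise, for example, if subjects who leave after lesion regression and continue pembrolizumab outside the trial are counted as having subsequent therapy. The SAP does not say whether they are.

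In subjects, for the roughly 20 planned in Protocol 12.1, the first line corresponds to an expected 20 × 0.424 = 8.5 with later therapy, of whom 20 × 0.019 = 0.4 are responders. It leaves 20 × 0.576 = 11.5 without, of whom 20 × 0.171 = 3.4 are responders.

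**The case against.** The strongest reply is that very little hangs on this row. The plot is conditional on sufficient data, and the list names what the subgroups could be. The subgroup summaries that 7.4.6.8 actually names are by combined positive score and HPV status. With about 20 evaluable subjects, and Protocol 12.2 allowing analyses to be dropped where data are limited, the row may never appear. SAP 7.4.6.1 and 7.4.6.6 describe all results as descriptive, with no formal comparisons. All of that stands, and it is why the point ranks low. It does not make the row interpretable if it is produced: an informational interval does nothing about conditioning on a consequence of the outcome. SAP section 4 also says that analyses are described in advance so that post hoc choices do not affect interpretation.

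A reader might go further and infer that the two groups are bound to differ, with later therapy always marking non-responders. The documents do not support that. Non-response and progression are an obvious route, but subjects also stop for toxicity or at their own request, responders can progress later, and the regression exit in Protocol 9.4.2.3 runs the other way. An illustration in which no responder ever starts new therapy (0% against 31.9% at an ORR of 0.19 with 50% uptake in non-responders) is an extreme case and not a forecast.

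A reader might also infer that the group without later therapy is seriously misclassified, because the current protocol's schedule (Table 2-1) has no visit after EOT. Some under-recording is possible. However, the SAP still describes follow-up every 8 weeks, Protocol 10.3.6 provides for recording new anti-cancer treatment after EOT, and serious adverse event reporting can run to 90 days after pembrolizumab (Protocol Table 10-1). The documents do not show how many subjects would be affected.

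**Conclusion.** The point holds as a low-severity improvement. Subsequent therapy is the only post-baseline item in the ORR forest-plot list. It generally arises after response has been observed and can depend on it, so an ORR difference across that row cannot be read as a difference in who benefits.

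Direction and size are unknown. Under a single true ORR of 0.19, the assumed uptake rates move the gap from about 25 percentage points in one direction (29.7 − 4.5 = 25.2), through zero, to 12.5 points in the other (26.0 − 13.5). These figures rest wholly on the assumed rates and show only that a gap can appear without any heterogeneity.

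Nothing here touches the overall ORR or its Clopper-Pearson interval in SAP 7.4.4, and it would be wrong to conclude that the primary result is compromised.

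**What to change.** In SAP 7.4.6.8, delete subsequent therapy from the ORR forest-plot list and state that the plot is limited to baseline characteristics. Report subsequent therapy descriptively instead, for example as a listing or a count beside overall survival, where Protocol 10.5 already recognises that it affects interpretation. That report should say what counts as subsequent therapy, including whether pembrolizumab continued outside the trial does.

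The cost is a short text edit and one simple descriptive display of data already collected. Sample size, error rates, the overall ORR and its interval are unchanged, and no valid subgroup information is lost.
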